3.2. Study Rationale

This is an open-label study to evaluate the reliability of using microdoses (less than 10 μ g) of radiotracer [¹⁸F]GTP1 for the evaluation of the whole-body biodistribution of the tracer in 6 healthy Japanese subjects (with at least 1 male and 1 female). Evaluating a small number of healthy subjects is standard to develop dosimetry calculations and to evaluate safety and tolerability. While [¹⁸F]GTP1 dosimetry studies and safety studies have been performed in healthy subject populations, the dosimetry and safety of [¹⁸F]GTP1 have not been specifically studied in Japanese subjects.

The development of a PET tracer for tau offers the possibility to utilize such an agent toward the development of investigational therapies and the further understanding of the pathophysiology of AD and other tauopathies and could therefore provide a societal benefit by accelerating the development of new treatments for AD and other tauopathies.

There is no direct benefit to subjects who participate in this protocol.

3.3. Risk/Benefit for this Study

There may be unknown risks to [¹⁸F]GTP1, but given that the investigational agent will be administered as a single microdose, the risk for a pharmacological effect is considered to be minimal. The potential benefit of the agent is the availability of a radiotracer targeting tau protein offering the possibility of improvement in diagnostic accuracy of AD and for measuring changes in tau with novel AD therapies. The primary risk associated with this study involves radiation exposure. The tracer doses used in this study and the experience of the Investigators in the execution of PET studies in humans in addition to the potential benefit of the [¹⁸F]GTP1 ligand for diagnostic uses make the relative risk/benefit ratio quite favorable.

4. POPULATION

The Investigator will ensure that all subjects being considered for the study meet the eligibility criteria. Subject selection is to be established by checking through all inclusion/exclusion criteria at screening and at the imaging visit. A relevant record (eg, checklist) will be stored with the source documentation at the study site.

The study population will be composed of healthy Japanese subjects (with at least 1 male and 1 female). Subjects will be enrolled until up to 6 evaluable subjects complete the study.

4.1. Inclusion Criteria

Subjects eligible for inclusion in this study only if they meet **all** the following criteria:

- Understand the study procedures and agree to participate by providing written informed consent.
- Are willing and able to comply with all study procedures and restrictions.
- Are males or females ≥ 18 years of age.
- Are in good health as determined by the Investigator based on clinical evaluations including past medical history, physical examination, vital signs, ECG, and laboratory tests at screening and prior to radiopharmaceutical administration.
- For women of childbearing potential, agreement to remain abstinent (refrain from heterosexual intercourse) or use contraception, and agreement to refrain from donating eggs, as defined below:
 - A woman is considered to be of childbearing potential if she is postmenarchal, has not reached a postmenopausal state (12 continuous months of amenorrhea with no identified cause other than menopause), and is not permanently infertile due to surgery (ie, removal of ovaries, fallopian tubes, and/or uterus) or another cause as determined by the Investigator (eg, Müllerian agenesis). The definition of childbearing potential may be adapted for alignment with local guidelines or regulations.
 - Women of childbearing potential must remain abstinent or use contraceptive methods with a failure rate of $<1\%$ per year during the treatment period and for 30 days after the

final dose of [¹⁸F]GTP1. Women must refrain from donating eggs during this same period.

- Examples of contraceptive methods with a failure rate of <1% per year include bilateral tubal ligation, male sterilization, hormonal contraceptives that inhibit ovulation, hormone-releasing intrauterine devices, and copper intrauterine devices.
- The reliability of sexual abstinence should be evaluated in relation to the duration of the clinical trial and the preferred and usual lifestyle of the subject. Periodic abstinence (eg, calendar, ovulation, symptothermal, or postovulation methods) and withdrawal are not adequate methods of contraception. If required per local guidelines or regulations, locally recognized adequate methods of contraception and information about the reliability of abstinence will be described in the local informed consent form.
- Male subjects with partners of childbearing potential must commit to the use of two methods of contraception, one of which is a barrier method (ie, condom), for the study duration and 90 days after the last dose.
- Male subjects must not donate sperm for the duration of the study and for 90 days after the last dose.
- Subjects must have both Japanese parents and all Japanese grandparents (self-reported).

4.2. Exclusion Criteria

Subjects fulfilling **any** of the following criteria are not eligible for inclusion in this study:

- The subject has a clinically significant abnormal laboratory value and/or clinically significant unstable medical or psychiatric illness.
- The subject is currently exposed to nicotine products or had regular nicotine exposure within a six-month period, to be verified by urine cotinine screening.
- History of drug or alcohol abuse within 12 months prior to screening, or evidence of such abuse as indicated by the laboratory assays conducted during the screening visit.
- The subject has evidence of clinically significant GI, cardiovascular, hepatic, renal, hematological, neoplastic, endocrine, neurological, immunodeficiency, pulmonary, or other disorder or disease.
- Prior participation in other research protocols or clinical care in the last year in addition to the radiation exposure expected from participation in this clinical study, such that radiation exposure exceeds the effective dose of 50 mSv, which would be above the acceptable annual limit established by the US Federal Guidelines.
- Use of any prescription drugs (except approved forms of birth control noted in Section 5.2.3), herbal supplements, within four weeks prior to initial dosing.
- Use of over the counter (OTC) medication (except acetaminophen), dietary supplements, or vitamins, within two weeks prior to initial dosing.
- Has a known hypersensitivity to any component of the formulation of [¹⁸F]GTP1 or related compounds.

- Major surgery, or donation or loss of 400 mL or more of blood within four (4) weeks prior to initial dosing, or longer if required by local regulation.
- Have a history or presence of any significant cardiovascular, respiratory, hepatic, renal, GI, endocrine, or neurological disorders which, in the opinion of the Investigator, are capable of altering the absorption, metabolism, or elimination of drugs or posing a health risk to participate in the study.
- History of immunodeficiency diseases, including a positive HIV test result.
- A positive Hepatitis B surface antigen (HBsAg) or Hepatitis C antibody test result.
- Positive pregnancy test result, if female. Women without documentation of non-childbearing potential will also receive pregnancy testing.
- Women who are lactating and breastfeeding.
- Unsuitable veins for repeated venipuncture.
- Subject is, in the opinion of the Investigator, unsuitable in any other way to participate in this study.

5. TREATMENT

5.1. Investigational Agent

[¹⁸F]GTP1 is a clear solution formulated for IV injection. [¹⁸F]GTP1 is formulated in 0.9% sodium chloride injection containing ethanol and sodium ascorbate. The final product bears a label with the following items: total activity (mCi), volume (mL), strength (mCi/mL), calibration date and time, batch number, study ID and shelf life. [¹⁸F]GTP1 will be stored at ambient temperature in its original container.

[¹⁸F]GTP1 is supplied as a sterile non-pyrogenic solution in sterile borosilicate glass vials with gray butyl septa and aluminum ring seals. The vial is contained within an outer lead or tungsten shield (“pig”) to protect from γ radiation.

5.2. Treating the Subject

5.2.1. Study Drug Supply and Storage

The investigational agent, the radiopharmaceutical [¹⁸F]GTP1, will be produced in the Invicro radiochemistry facility at [name]. Quality control testing includes strength by gamma assay, radiochemical purity and identity (HPLC), drug mass and total impurity quantification, pH, visual inspection, pyrogenicity and sterility by compendial tests. The final drug product is provided as a clear, sterile solution in a 30 mL glass vial. The vial is contained within a secondary lead or tungsten radiation shield and may be stored upright at ambient temperature and humidity until administration. The investigational agent must be used within the expiration time (10 hours).

5.2.2. Administration of Investigational Agent

Study center personnel will administer [¹⁸F]GTP1 IV as a bolus injection. Prior to PET imaging, subjects will have an IV catheter (for radiotracer administration) inserted according to standard clinical practice. Each subject will receive a single injection of [¹⁸F]GTP1. The radioligand, [¹⁸F]GTP1, will be injected IV at a dose of not more than 370 MBq (≤10 mCi), with a maximum drug mass dose of 10 µg and maximum volume of 10 mL. The injection will occur as a bolus followed by a 10 mL saline flush. Qualified study staff will accompany subjects during PET imaging procedures.

5.2.3. Concomitant Treatment

Use of any prescription drugs, herbal supplements, within four (4) weeks prior to initial dosing, and/or OTC medication, dietary supplements (vitamins included) within two (2) weeks prior to initial dosing is prohibited. Approved forms of prescription birth control (hormonal contraceptives, hormone-releasing intrauterine devices, and copper intrauterine devices) are not prohibited and will be documented as a concomitant medication. If needed (ie, an incidental and limited need), acetaminophen is acceptable, but must be documented as a concomitant medication/significant non-drug therapy.

5.2.4. Discontinuation of Study Treatment and Premature Subject Withdrawal

The study will be stopped, and no further dosing will occur, pending a full safety review if one or more study drug related SAEs are reported. If a subject withdraws or discontinues the study for any reason, the subject will be replaced until there are up to (with at least 1 male and 1 female) evaluable subjects.

Subjects may voluntarily withdraw from the study for any reason at any time. They may be considered withdrawn if they state an intention to withdraw, fail to return for visits, or become lost to follow-up for any other reason.

If premature withdrawal occurs for any reason, the Investigator must make every effort to determine the primary reason for a subject's premature withdrawal from the study and document this information in the study source.

Subjects may develop AEs or abnormalities in vital signs, ECG, physical examination, or laboratory determinations during their participation in the study. If these occur, the Investigator may discontinue a subject from the study if, in his/her clinical judgment, continued participation would result in undue risk or further worsening of the condition.

For subjects who are lost to follow-up (ie, those subjects whose status is unclear because they fail to appear for study visits without stating an intention to withdraw), the Investigator should show due diligence by documenting attempts to contact the subject, eg, dates of telephone calls, registered letters, or other attempts to communicate.

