7.1.2. SAE Definition

An SAE is defined as an event which:

- is fatal or life-threatening
- constitutes a congenital anomaly/birth defect

- results in persistent or significant incapacity or substantial disruption of the ability to conduct normal life functions
- is medically significant, ie, defined as an event that jeopardizes the subject or may require medical or surgical intervention to prevent one of the outcomes listed above
- requires in-patient hospitalization or prolongation of existing hospitalization, unless hospitalization is for:
 - routine treatment or monitoring of the studied indication, not associated with any deterioration in condition
 - elective or pre-planned treatment for a preexisting condition that is unrelated to the indication under study and has not worsened since the start of study drug

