7.1.3. Adverse Events of Special Interest Definition

Adverse events of special interest (AESI) are required to be reported by the investigator to the Sponsor immediately (ie, no more than 24 hours after learning of the event; see Section 7.2 for reporting instructions). AESI for this study are as follows:

- Cases of potential drug-induced liver injury that include an elevated ALT or AST in combination with either an elevated bilirubin or clinical jaundice, as defined by Hy's Law
 The finding of an elevated ALT or AST (> 3 ULN) in combination with either an elevated total bilirubin (2 ULN) or clinical jaundice in the absence of cholestasis or other causes of hyperbilirubinemia is considered to be an indicator of severe liver injury (as defined by Hy's Law). Therefore, investigators must report as an AE the occurrence of either of the following:
 - Treatment-emergent ALT or AST > 3x ULN in combination with total bilirubin >2 x ULN
 - Treatment-emergent ALT or AST > 3 x ULN in combination with clinical jaundice

The most appropriate diagnosis or (if a diagnosis cannot be established) the abnormal laboratory values should be recorded on the Adverse Event eCRF and reported to the Sponsor immediately (ie, no more than 24 hours after learning of the event), either as a SAE or an AESI.

- Suspected transmission of an infectious agent by the study drug, as defined below
 Any organism, virus, or infectious particle (eg, prion protein transmitting transmissible spongiform encephalopathy), pathogenic or non-pathogenic, is considered an infectious agent. A transmission of an infectious agent may be suspected from clinical symptoms or laboratory findings that indicate an infection in a subject exposed to a medicinal product. This term applies only when a contamination of the study drug is suspected.

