7.1.6. Relationship of AEs to the Study Drug

The Investigator will document his/her opinion of the relationship of the AE to treatment with the study drug (Table 3).

Table 3: Relationship of AEs to Study Drug

Relationship	Description
Yes	A reaction that follows a reasonable temporal sequence from administration of the drug or in which the drug level has been established in body fluids or tissue; that follows a known or expected response pattern to the suspected drug; and that is confirmed by improvement on stopping or reducing the dosage of the drug, and reappearance of the reaction on repeated exposure.
No	An AE will be considered related, unless it fulfills the criteria specified below: Evidence exists that the AE has a cause other than [¹⁸ F]GTP1 (eg, preexisting medical condition, underlying disease, intercurrent illness, or concomitant medication). AND/OR The AE does not have a plausible temporal relationship with [¹⁸ F]GTP1 administration.

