7.2. Serious Adverse Event and Adverse Event of Special Interest Reporting

To ensure subject safety, every SAE and AESI, regardless of suspected causality, occurring after the subject has provided informed consent and until the subject has completed the study must be reported to the study sponsor within 24 hours of learning of its occurrence.

SAEs that occur later than the Follow-up Phone Call will not require reporting unless the Investigator believes the event(s) were related to either the investigational study drug or study procedures.

Recurrent episodes, complications, or progression of the initial SAE/AESI must be reported as follow-up to the original episode, regardless of when the event occurs. This report must be submitted within 24 hours of the Investigator receiving the follow-up information. An SAE/AESI that is considered completely unrelated to a previously reported one should be reported separately as a new event. New signs or symptoms or a change in the diagnosis, significant new diagnostic test results, change in the event's outcome, including recovery, additional information on the clinical course of the event should also be submitted immediately.

All SAE/AESIs, regardless of causality, will be reviewed by the study sponsor.

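### The mandatory dosing hold in Section 5.2.4 does not cover suspected contamination of the study drug when the resulting event is judged non-serious

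*Combined protocol and SAP*

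**What the plan says.** Section 5.2.4 of the combined protocol and SAP halts the study, and "no further dosing will occur, pending a full safety review if one or more study drug related SAEs are reported". AESIs are not mentioned there.

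Section 7.1.3 lists two AESIs: Hy's Law liver cases and suspected transmission of infection by the study drug. For the second, any organism, virus or infectious particle, "pathogenic or non-pathogenic, is considered an infectious agent". Transmission "may be suspected from clinical symptoms or laboratory findings that indicate an infection in a subject exposed to a medicinal product". The definition then narrows: "This term applies only when a contamination of the study drug is suspected".

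For an AESI, Sections 7.1.3 and 7.2 require a report to the sponsor within 24 hours of learning of the event, follow-up information on the same timescale, and review: "All SAE/AESIs, regardless of causality, will be reviewed by the study sponsor". Neither section attaches any dosing action.

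**The concern.** A study-level hold protects people who have not yet been dosed. For most adverse events, how badly the first subject was affected is a reasonable guide to the risk for the next one, so tying the hold to seriousness makes sense. Suspected contamination is different. The suspected hazard lies in the product, and a mild illness in one subject does not show that the next injection is safe. Those next in line are healthy volunteers who, as Section 3.2 says, gain no direct benefit. The protocol treats the event as urgent enough for 24-hour reporting, yet does not say that the next injection must wait for the outcome of the review.

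**Working it through.** No arithmetic is needed to establish the gap, and the protocol gives no figure to reproduce. The check sets the conditions of the relevant sections side by side.

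1. **What triggers the hold (5.2.4).** Two conditions must both be met: the event is serious, and it is related to the study drug.

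2. **What triggers the AESI (7.1.3).** Symptoms or laboratory findings must indicate an infection in an exposed subject, and contamination of the product must be suspected. Seriousness is not a condition.

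3. **Can the AESI be non-serious?** The most likely route to seriousness in Section 7.1.2 is an event that "is medically significant, ie, defined as an event that jeopardizes the subject or may require medical or surgical intervention" to avert one of the listed serious outcomes. A mild, self-limiting infection can fall short of that, and the decision is a matter of judgement.

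4. **Does default relatedness close the gap?** Section 7.1.6 says: "An AE will be considered related, unless it fulfills the criteria specified below". This normally supplies the relatedness condition, but the missing condition is seriousness.

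| Contamination AESI | Serious (7.1.2) | Related (7.1.6) | 24-hour report and sponsor review (7.2) | Mandatory hold (5.2.4) |
|---|---|---|---|---|
| Judged serious | yes | yes, by default | yes | yes |
| Judged non-serious | no | yes, by default | yes | **no** |

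5. **Does another provision fill the gap?**
   - Section 5.2.4 also lets the investigator discontinue a subject, but this is discretionary and concerns that one subject.
   - Section 7.1.5 lists actions for an individual's adverse event.
   - The Synopsis (Procedures) cancels a scan for synthesis failure or camera problems only.
   - Section 5.2.1 lists quality control that includes "visual inspection, pyrogenicity and sterility by compendial tests". It does not say whether sterility results are known before injection, and it links no result to a study hold.

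   The count of mandatory study-level hold triggers is therefore 1, and the count tied to an AESI is 0.

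6. **How would the signal arise?** After injection, the scheduled laboratory tests are hematology, chemistry and dipstick urinalysis at the end of imaging (Section 6.1.2). Serology is done at screening only (Schedule of Assessments, footnote 5), and no culture is scheduled. Under Section 7.1.1 an abnormal laboratory value is an adverse event only if it causes signs or symptoms, is considered clinically significant, or needs therapy. The usual signal would therefore be symptoms, seen at the visit or reported afterwards. The only scheduled contact after discharge is the call at 4 ± 2 days (Section 6.1.3), that is, from day 4 − 2 = 2 to day 4 + 2 = 6. No minimum interval between subjects is stated.

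Appendix 3 records that the AESI section was added in Amendment 2 and lists no change to Section 5.2.4. That fits the finding, which rests on the current text alone.

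**The case against.** The best defence is that the existing rule already catches what matters. An infection attributed to a contaminated intravenous injection is a strong candidate for the medically significant criterion. With relatedness supplied by default, the hold would then apply. What remains is a mild infection that is both blamed on the product and judged not to jeopardize the subject. Even then the sponsor hears within 24 hours and is free to pause. Subjects with an adverse event are not discharged until it resolves or stabilizes (Section 6.1.2), and new symptoms that need assessment bring them back to the clinic (Section 6.1.3). Manufacture is under GMP and an IND, and a batch expires in 10 hours (Section 5.2.1), so a subject dosed on a later day would not receive the suspect batch.

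All of this stands, and it makes the gap small without closing it. Section 5.2.4 chose a mandatory rule over sponsor discretion for related SAEs, and the same reasoning applies to a suspect injectable product. Quarantining the affected batch would be a narrower remedy, but given the 10-hour expiry the remaining concern is a production fault that carries over to the next batch, which quarantine does not address.

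Two stronger readings are tempting but unsupported:
- **That the whole AESI class escapes the hold.** Section 7.1.3 calls the Hy's Law finding an indicator of severe liver injury, so such a case would normally already be an SAE.
- **That any stray laboratory result or harmless organism would qualify.** The definition requires findings that indicate an infection together with suspected contamination of the product, and Section 7.1.1 limits which laboratory values count as adverse events.

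**Conclusion.** The point holds in a narrow form and is worth considering. Followed as written, the protocol allows the next healthy volunteer to be injected while product contamination is suspected, provided the event that raised the suspicion was judged non-serious. The rule is stated clearly; its trigger is too narrow for this one event.

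The size is small, and the documents give no basis for a probability. A reader might count the subjects not yet dosed at the time of the report, out of up to 6 evaluable, and treat that as the number at risk. The documents do not support this: the count would be the same for any proposed stopping trigger and says nothing about how likely contamination is. Nor would a hold help anyone dosed before the report arrived.

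The conclusion assumes that a non-serious contamination AESI can occur, which the wording of Sections 7.1.2 and 7.1.3 allows. It also assumes that pages outside the public text, including any part of Section 1 after Section 1.1, contain no further hold.

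**What to change.** In Section 5.2.4, keep the sentence and add a second trigger directly after the reference to related SAEs: *or any suspected transmission of an infectious agent by the study drug (Section 7.1.3)*. The stop and the full safety review then apply to both triggers. Sections 7.1.3 and 7.2 need no change, and neither do the endpoints, sample size or analyses.

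The cost is a protocol version update, as with the changes in Appendices 2 and 3, and a possible short scheduling delay if a suspicion proves unfounded. A longer review could take a screened subject past the 30-day window before imaging. No subject's treatment would be interrupted, because each receives a single injection (Section 5.2.2).
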